2.4 Determination of Sample Size

No sample size calculation was done. Sample size was dependent upon recruitment into and completion of preceding studies. At the time of development of this SAP amendment 1, the enrollment into this study has been completed; a total of 859 subjects were enrolled into N01125 including 6 subjects entering the study from N01315.

3 DATA ANALYSIS CONSIDERATIONS

3.1 General presentation of summaries and analyses

Statistical analysis and generation of tables, figures, subject data listings, and statistical output will be carried out using SAS® Version 9.1 or higher.

Descriptive statistics, such as the mean, standard deviation (SD), median, 25th percentile, 75th percentile, minimum value, and maximum value for quantitative variables, and counts and percentages for categorical variables, will be provided. Denominators for percentages will generally be based on the set of subjects with at least 1 assessment at the time point or at least 1 assessment during the time interval being summarized.

All summaries will be descriptive; no statistical hypothesis testing is planned.

Unless otherwise noted, summaries will present BRV overall, which will include all subjects exposed to BRV during the study.

Subject data listings will be provided and will present source data and key derived variables for statistical analyses.

3.2 Analysis time points

3.2.1 First and last dose of BRV

Unless otherwise noted, all references to the first dose of BRV in this SAP refer to the first dose of BRV during N01125 (ie, not the first dose of BRV from the previous study in which subjects participated in prior to N01125). Unless otherwise noted, all references to the last known dose of BRV in this SAP refer to the last dose of BRV taken across any study periods (ie, the last dose of BRV across both the Evaluation and Down-Titration Periods).

3.2.2 Relative day

Relative day will be calculated as the current date minus the date of first dose of study drug for days prior to the first dose of study drug, and the current date minus the date of first dose

of study drug plus 1 for days on or after the day first dose of study drug and prior to or on the day of last study drug dose (eg, the day of first dose will be Day 1 and the day prior to first dose will be Day -1), ie, Day 1 representing the day of first dose of BRV, the previous day is Day -1 and each day prior to that is Day -2, Day -3, etc; subsequent relative days to Day 1 will be Day 2, Day 3, etc. For days after the last dose of BRV, relative day will be calculated as the current date minus the date of last dose of BRV and including a '+' to denote post treatment days (eg, the day after the last dose of BRV will be Day +1). Relative day will not be calculated for partial or missing dates.

3.2.3 Summaries at Study Entry

Study Entry denotes an analysis time point that will summarize assessments done at the last visit of the previous study for most subjects as described below, but may also include assessments that may have been performed at Supplemental Entry Visits (SEVs) for some subjects who did not immediately enter N01125.

There are 4 groups of subjects to consider:

1. Subjects who immediately entered N01125 after completing the Treatment Periods for N01252 and N01254 or the blinded Conversion Periods for N01114, N01187, and N01236
2. Subjects who entered the Down-Titration Period of the previous study and entered N01125 during the Down-Titration Period
3. Subjects who did not immediately enter N01125 and had a gap in treatment with study drug between the previous study and N01125 Subjects
4. Subjects entering the study from N01315 who entered after their N01315 study sites were closed

Subjects in Categories 1 and 2

Subjects in categories 1 and 2 will generally not have any interruption in study drug dosing during the transition to N01125. For such subjects, selected assessments from the following visits from the previous study will be summarized at Study Entry:

Study	Visit (Time Point)
N01187/N01236	Visit 9 (Week 16)
N01114	Visit 10 (Week 12)
N01252	Visit 7 (Week 12)
N01254	Visit 8 (Week 16)

The following assessments were to be performed for all subjects at the above time points: laboratory parameters, vital signs, and ECGs; these assessments will be summarized at Study Entry. The following assessments were to be performed for all subjects from N01252 and N01254 at the above time points: QOLIE-31-P, HADS, EQ-5D and socio-professional data; however, these assessments will not be summarized at Study Entry.

Subjects in Category 3

Some subjects in category 3 have data available from an SEV at the time of entry into N01125. Laboratory parameters, vital signs, and ECGs collected at SEV will be summarized

at Study Entry. If one or more of these assessments were not performed at SEV, or if a subject in category 3 does not have an SEV, then the subject will be excluded from summaries of Study Entry for the assessments that were not performed.

Subjects in Category 4

Subjects in category 4 will have their demographic data including date of birth, country, gender, race, and ongoing medication data transferred into N01125. Laboratory parameters, vital signs, and ECGs collected at SEV will be collected at Study Entry.

3.2.4 Study periods

The study is divided into 3 periods: Evaluation Period, Down-Titration Period, and Post-Treatment Period. A subject is classified as “discontinued” if the subject has a termination case report form (CRF) or has an early discontinuation visit (EDV). A subject is classified as “completed” if this subject completes the full extent of the study as defined in the protocol at database lock.

A “discontinued” subject can be potentially slotted into the 3 periods of the study. The following algorithms will be used to slot the subject appropriately into the Evaluation Period, Down-Titration Period, and Post-Treatment Period.

- For Evaluation Period, the start date is the date of first dose of BRV, and the following algorithm is used to determine the end date:
 - If the subject enters the Down-Titration Period, then the date of EDV is the end date;
 - If the subject does not enter the Down-Titration Period but meets 1 of the following criteria, the Evaluation Period ends on date of last dose of BRV,
 - Without an EDV but having a termination CRF,
 - With an EDV and having a termination CRF,
 - With an EDV and the date of EDV prior to the database lock date and having no termination CRF.
- A subject is considered entering Down-Titration Period only if the subject has an EDV and at least 1 dose of study drug after the date of EDV, the start date of Down-Titration Period is set as 1 day after the date of EDV, and the Down-Titration Period ends on date of last dose of BRV. A subject without an EDV but having a termination CRF or with an EDV but without any dosing of study drug after the EDV will not have the Down-Titration Period, and no artificial Down-Titration Period will be created for analysis.
- A subject is considered entering the Post-Treatment Period if the subject has at least 1 contact (scheduled visit, unscheduled visit, or telephone contact) after the date of last dose of BRV. The Post-Treatment Period starts 1 day after date of last dose of BRV irrespective of entering the Down-Titration Period, and there is no end date.

A “completed” subject can potentially have Evaluation Period, Down-Titration Period, and Post-Treatment Period. At the time of study termination by the Sponsor, subjects will discontinue the study drug following the down titration process or will be converted without titration to commercial BRV where available; alternatively, subjects may be initiated without down-titration in a managed access program, named patient program, compassionate use program, or similar type of access program as allowed per country specific requirements in addition to legal and regulatory guidelines.

3.2.5 Monthly time intervals

A month is defined as 30 days and time intervals based on monthly durations are defined as a multiple of 30 days (eg, 12 months is defined as 360 days). The following definitions of 3-month and 6-month intervals are based on 30-day months where the date of first dose of BRV is Day 1:

Interval	Duration Definition
Months 1-3	Days 1-90
Months 4-6	Days 91-180
Months 7-9	Days 181-270
Months 10-12	Days 271-360
Months 1-6	Days 1-180
Months 7-12	Days 181-360
Months 13-18	Days 361-540
Months 19-24	Days 541-720

Subsequent 3- and 6-month intervals are defined in a similar manner.

Six-month intervals are defined for the evaluation of direct and indirect cost parameters. Statistical summaries for direct and indirect cost parameters will only present results through the first 2 years of treatment. Three-month intervals will be used for analysis of efficacy outcomes and AEs.

For the analysis of efficacy outcomes, a subject is included in the analysis for a 3-month interval if the end date is on or after the *last day* of the 3-month interval and the subject diary was completed for at least 1 day during the 3-month interval.

For the analysis of AEs, a subject is included in the analysis for a 3-month interval if the end date is on or after the *first day* of the 3-month interval.

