13.3 Statistical and Analytical Issues

13.3.1 Handling of Dropouts or Missing Data

Safety and efficacy variables will be analyzed as they are available. Days with missing information will be ignored in the calculation of the seizure frequency and seizure days.

confidential information and ucb property

This document cannot be used to support any marketing authorization application and any extensions or variations thereof.

Since subjects will drop out at different times from the study, results will be presented by categories of duration of exposure.

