3.8.1.2 Calculation of adjusted seizure frequency

The following derivations apply only to subjects with Partial Onset Seizures.

Baseline POS frequency for seizure types I, IA, IB, IC, and for all seizure types (I+II+III) will be obtained from the Baseline Period of the previous double-blind study.

The total number of seizures for seizure types I, IA, IB, and IC, and the total number of seizures for all seizure types (I+II+III) will be calculated overall, by 3-month time intervals, and over the cohort interval for each exposure duration cohort. All seizure diary on or after the date of first dose of BRV and prior to or on the date of last dose of BRV will be considered for these calculations.

Twenty-eight day adjusted seizure frequency for seizure types I, IA, IB, and IC, and for all seizure types (I+II+III) will be calculated overall, within each 3-month time interval, and over each exposure duration cohort interval by dividing the total number of seizures for each seizure type by the number of days for which the diary was completed overall, within each 3-month interval, and within each exposure duration cohort interval, and multiplying the resulting value by 28.

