8.1.3 Responder outcome for POS frequency

Responders over the On Treatment Period are defined as subjects with a 50% or greater reduction in 28-day adjusted POS frequency from Baseline to the On Treatment Period. A similar calculation applies to each 3-month time interval over the On Treatment Period and for the cohort interval for each exposure duration cohort.

The number and percentage of responders for POS frequency will be summarized for the On Treatment Period, and by 3-month time intervals over the On Treatment Period. The summary over the On Treatment Period will include all subjects in the POS Efficacy Analysis Set. Similar summaries will be provided over the full cohort interval and by 3-month time intervals for each exposure duration cohort. Responder rates for POS frequency will be summarized in the same manner by geographic region.

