11.2.2 General summaries of TEAEs

Pre-treatment AEs will be provided in a subject data listing; no summaries of pre-treatment AEs are planned.

An overall summary of AEs will provide the overall number of TEAEs and the numbers and percentages of subjects with at least 1 TEAE, with a TEAE that led to permanent discontinuation of study drug, with a drug-related TEAE, with a severe TEAE, with a treatment-emergent SAE, and with a drug-related treatment-emergent SAE. The number and percentage of subjects who died will also be summarized. This summary will be provided for all subjects in the Safety Analysis Set and also by subgroup for geographic region and indication.

The following summaries of TEAEs will be provided by MedDRA SOC and PT. All summaries are for the combined Evaluation, Down-Titration, and Post-Treatment Periods unless otherwise indicated.

Overall Incidence Summaries

- Incidence of TEAEs
- Incidence of TEAEs by 3-month time interval
- Incidence of TEAEs by study period (Evaluation, Down-Titration, Post-Treatment)
- Incidence of TEAEs for TEAEs occurring in at least 5% of subjects

- Incidence of TEAEs by 3-month time intervals for TEAEs occurring in at least 5% of subjects overall
- Incidence of non-serious TEAEs occurring in at least 5% of subjects

The incidence of TEAEs occurring in at least 5% of subjects will be summarized overall as noted above and also by subgroup for geographic region, indication, and randomized treatment from the previous double-blind study.

A subject is included in a 3-month interval if the subject was receiving BRV at any time during that interval based on their duration of exposure to BRV (eg, a subject with exposure for 91 days is included in the time interval for Months 1-3 and Months 4-6). Summaries of AEs by 3-month intervals will include all subjects who are classified into each time interval as defined above. TEAEs which had onset prior to or on the date of the last dose of BRV are included in summaries by 3-month time intervals.

Maximum Intensity and Causality

- Incidence of TEAEs by maximum intensity
- Incidence of drug-related TEAEs

Serious Adverse Events

- Incidence of treatment-emergent SAEs

Discontinuations due to TEAE

- Incidence of TEAEs leading to permanent discontinuation of study drug

TEAEs of interest

AEs of interest will be identified based on MedDRA search criteria, which are documented outside of the SAP. The following summaries will be provided for AEs of interest:

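### One completed diary day in 90 is enough for a subject to count in a 3-month efficacy interval, so interval frequency, percent reduction and responder status can rest on uninformative data

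*SAP*

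**What the plan says.** SAP 3.2.5 fixes the interval length: "A month is defined as 30 days and time intervals based on monthly durations are defined as a multiple of 30 days", so a 3-month interval is 90 days. The efficacy rule has two parts. Retention is judged at the interval's last day: "For the analysis of efficacy outcomes, a subject is included in the analysis for a 3-month interval if the end date is on or after". On the diary, the same sentence ends with "3-month interval and the subject diary was completed for at least 1 day during the 3-month interval", so one completed day is enough.

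For adverse events the same section judges the end date against the interval's first day: "For the analysis of AEs, a subject is included in the analysis for a 3-month interval if the end date is on or after". SAP 11.2.2 agrees: "A subject is included in a 3-month interval if the subject was receiving BRV at any time during that interval".

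SAP 3.8.1.2 computes the rate as seizures divided by completed diary days, overall, "within each 3-month interval, and within each exposure duration cohort interval, and multiplying the resulting value by 28". SAP 8.1.3 defines a responder by a reduction of at least 50% from Baseline and adds: "A similar calculation applies to each 3-month time interval over the On Treatment Period". Percent reduction (8.1.2) is handled in the same way, and the PGS seizure-day outcomes follow the same pattern (8.2.2).

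Three other provisions matter:
- SAP 8.2.1.1 requires the diary to be complete on at least 90% of days before a subject can be called seizure free.
- SAP 4.2 plans no summaries of the impact of missing diary days. It introduces exposure duration cohorts because dropouts may influence long-term results.
- SAP 8.1.1 to 8.1.3 keep every subject of the POS Efficacy Analysis Set in the On Treatment summary, and repeat the 3-month tables within each exposure duration cohort.

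**The concern.** The secondary objective is maintenance of efficacy over time, and the 3-month tables are where a reader will look for it. Two features of the inclusion rule affect them.

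First, the 28-day standardisation gives a number for any count of diary days, however small. A one-day rate is either 0 or a multiple of 28 seizures per 28 days, yet it enters the table with the same weight as a rate from 90 days. The SAP sets a 90% minimum for seizure freedom but nothing comparable for frequency, percent reduction or responder status. With no missing-diary summary planned, a reader could not see how much of a table rests on thin data.

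Second, a subject who stops part-way through an interval contributes nothing to it, even with up to 89 days of recorded on-drug diary. A subject who stops before Day 90 is in no interval at all. Lack of efficacy and loss of efficacy are among the discontinuation reasons in SAP 5.1, so the subjects left out may not be typical.

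**Working it through.** The documents give no baseline seizure rate, dropout rate or diary completeness, and no bias figure to reproduce. Those inputs below are assumptions, shown over a range. The interval length, rate formula, responder cut-off and inclusion rules come from the SAP sections cited above.

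**1. Diary minimum**

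Let b be baseline seizures per 28 days (taken as known), r the true on-treatment ratio to baseline, and m the completed diary days. With Poisson counts, the subject is classed a responder when the count X is at most 0.5 × b × m/28, where X has mean b × r × m/28.

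For b = 8 and no true change (r = 1):

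| Diary days | Mean count | Largest count classed responder | P(responder) |
|---|---|---|---|
| 1 | 0.286 | 0 | exp(−0.286) = 75.1% |
| 28 | 8 | 4 | 10.0% |
| 45 (50% of days) | 12.86 | 6 | 2.8% |
| 90 | 25.71 | 12 | 0.2% |

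On one day, percent reduction is 100% with no seizure. With one seizure it is 100 × (8 − 28)/8 = −250%.

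Other assumed baselines, no true change:

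| b | 1 day | 28 days | 90 days |
|---|---|---|---|
| 4 | 86.7% | 23.8% | 2.8% |
| 20 | 49.0% | 1.1% | 0.0% |
| 40 | 24.0% | 0.0% | 0.0% |

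The error does not always favour the drug. At b = 40 with a true 60% reduction (r = 0.4), a subject is classed a responder with probability 56.5% on one day and 96.2% on 90 days.

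Effect on a table: if a share s of an interval's subjects had one diary day, b = 8 and no true change, the responder rate would rise by s × (75.1 − 0.2) points. That is 0.75, 3.75 and 7.5 points for s = 1%, 5% and 10%. The actual share is not known.

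**2. Last-day rule within one interval**

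If a fraction d of those on drug at the interval's start stop within it, leaving them out changes the responder rate by d × (response in stayers − response in stoppers). With response in stayers assumed to be 45%:

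- d = 2%, stoppers 30%: 0.02 × 15 = +0.3 points
- d = 5%, stoppers 20%: 0.05 × 25 = +1.25 points
- d = 5%, stoppers 45%: 0
- Extremes at d = 15%: +6.75 points if no stopper responds, −2.25 points if stoppers respond at 60%

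**3. Last-day rule over eight intervals (24 months)**

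Assume 40% true responders, constant over time, with dropout per interval of hN in non-responders and hR in responders. After j intervals the responder share among those remaining is

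0.4(1 − hR)^j / [0.4(1 − hR)^j + 0.6(1 − hN)^j].

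The last-day rule uses j = k in interval k; a first-day rule uses j = k − 1.

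| hN / hR | Interval 1: last-day / first-day | Interval 8: last-day / first-day |
|---|---|---|
| 5% / 5% | 40.0 / 40.0 | 40.0 / 40.0 |
| 8% / 4% | 41.0 / 40.0 | 48.4 / 47.3 |
| 10% / 3% | 41.8 / 40.0 | 54.8 / 53.0 |

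For example, at 8%/4% and j = 8: 0.4 × 0.7214 / (0.4 × 0.7214 + 0.6 × 0.5132) = 48.4%.

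The last-day rule adds about 1.0 to 1.9 points to each interval. The much larger rise across intervals comes from attrition and appears under either rule, one interval apart. In a fixed cohort with at least 24 months of exposure, the rate would be constant at 48.4% in the 8%/4% case: no drift, but a selected group.

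**The case against.** The strongest reply is that the SAP already deals with dropout, and much of this stands.

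- **Data are not lost to the analysis.** Early stoppers' diary days leave one interval row but stay in the On Treatment summary. SAP 5.1 also reports discontinuation reasons and Kaplan-Meier retention.
- **The cohorts fix membership.** If the end date is the last dose, everyone in an exposure duration cohort reaches the last day of each interval up to the cohort's length, so the last-day rule removes nobody there.
- **There is no conflict with the protocol.** A reader might infer one from Protocol 13.3.1, "Safety and efficacy variables will be analyzed as they are available". That section goes on to plan results by category of exposure duration because subjects drop out at different times, and the SAP does this.
- **The AE rule is not a contradiction.** Incidence needs everyone at risk, while a 90-day rate can reasonably require a full interval.
- **Sparse diaries may be rare.** Protocol 10.2.12 has the diary discussed for completeness at each visit.
- **Any threshold is a judgement.** At b = 4, a 28-day minimum still leaves 23.8% false responders. It also keeps anyone with fewer than 28 diary days out of every interval.

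What the reply does not meet is narrower. Neither safeguard sets a diary minimum, so the one-day rule carries into the cohort tables. The cohorts describe only those who stayed. The On Treatment summary gives one value per subject and cannot show a time course.

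**Conclusion.** The point holds as a weakness in the interval rule. The diary part is the stronger one. With one day in 90 allowed, an unchanged subject at an assumed 8 seizures per 28 days is classed a responder 75% of the time, against 0.2% on a full diary. This rests on Poisson counts and a known baseline; the effect on any table depends on the unknown share of sparse diaries.

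The last-day part is modest: about 0.3 to 2 points if stopping is linked to poor response, zero if it is not, and negative if better responders stop more often.

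A reader might infer that the published time course is biased in brivaracetam's favour. The documents do not support that as a fact. They make a link between stopping and poor response plausible but give no figure for it, and most of any upward drift would come from attrition itself, which a first-day rule would not remove.

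All summaries are descriptive and efficacy is a secondary objective, so no test or sample size is affected. It should be changed because the correction is cheap.

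**What to change.** In SAP 3.2.5:

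1. Require a stated minimum of completed diary days for interval frequency or seizure days, percent reduction and responder status, for example 28 days or 50% of the interval (45 days). Keep the current one-day rule as a sensitivity table.
2. Beside the full-interval table, add a 3-month table with every subject on BRV on the interval's first day who meets the diary minimum. The 28-day standardisation in 3.8.1.2 already handles partial intervals.
3. Report the number of subjects and of completed diary days for each interval.
4. Define the end date used in the rule. SAP 3.2.4 can end the Evaluation Period at the Early Discontinuation Visit, while 3.8.1.2 uses diary data to the last BRV dose; 3.2.5 does not say which applies. The choice decides whether a subject still down-titrating on an interval's last day is counted.

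The cost is SAP wording, an inclusion flag and some extra tables from data already collected. Partial-interval values will be somewhat noisier, and a few subjects with sparse diaries will leave the interval tables; their diary days remain in the On Treatment estimate.
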